## 7.3. Participant Discontinuation/Withdrawal from the Study

- A participant may withdraw from the study at any time at his/her own request or may be withdrawn at any time at the discretion of the investigator for safety, behavioural, compliance or administrative reasons. This is expected to be uncommon.
- At the time of discontinuing from the study, if possible, an early discontinuation visit should be conducted (assessments in the follow-up visit), as shown in the SoA in Section 1.3. See SoA for data to be collected at the time of study discontinuation and follow-up and for any further evaluations that need to be completed.
- The participant will be permanently discontinued both from the study intervention and from the study at that time.
- If the participant withdraws consent for disclosure of future information, the sponsor may retain and continue to use any data collected before such a withdrawal of consent.
- If a participant withdraws from the study, he/she may request destruction of any samples taken and not tested, and the investigator must document this in the site study records.

## 7.4. Lost to Follow Up

A participant will be considered lost to follow-up if he or she repeatedly fails to return for scheduled visits and is unable to be contacted by the study site.

The following actions must be taken if a participant fails to return to the clinic for a required study visit:

- The site must attempt to contact the participant and reschedule the missed visit as soon as possible and counsel the participant on the importance of maintaining the assigned visit schedule and ascertain whether the participant wishes to and/or should continue in the study.
- Before a participant is deemed lost to follow up, the investigator or designee must make every effort to regain contact with the participant (where possible, 3 telephone calls and, if necessary, a certified letter to the participant's last known mailing address or local equivalent methods). These contact attempts should be documented in the participant's medical record.
- Should the participant continue to be unreachable, he/she will be considered to have withdrawn from the study.

Discontinuation of specific sites or of the study are handled as part of [Appendix 1](#).

## 8. STUDY ASSESSMENTS AND PROCEDURES

- Study procedures and their timing are summarized in the SoA.
- Protocol waivers or exemptions are not allowed.
- Immediate safety concerns should be discussed with the sponsor immediately upon occurrence or awareness to determine if the participant should continue or discontinue study intervention.
- Adherence to the study design requirements, including those specified in the SoA, is essential and required for study conduct.
- All screening evaluations must be completed and reviewed to confirm that potential participants meet all eligibility criteria. The investigator will maintain a screening log to record details of all participants screened and to confirm eligibility or record reasons for screening failure, as applicable.
- Procedures conducted as part of the participant's routine clinical management (e.g., blood count) and obtained before signing of ICF may be utilized for screening or baseline purposes provided the procedure met the protocol-specified criteria and was performed within the time frame defined in the SoA.
- If assessments are scheduled for the same nominal time, then the assessments should occur in the following order:
  1. 12-lead ECG
  2. Vital signs

3. Urine specimen collections
4. Pharmacokinetic and safety blood draws

Note: The timing of the assessments should allow the blood draw to occur at the exact nominal time.

- The maximum amount of blood collected from each participant over the duration of the study, including any extra assessments that may be required, will not exceed 500 mL in 56 days.
- Repeat or unscheduled samples may be taken for safety reasons or for technical issues with the samples.
- Time window allowances for all study assessments will be followed according to the time window allowances as indicated in the SRM.

## **8.1. Efficacy Assessments**

Not applicable.

## **8.2. Safety Assessments**

Planned time points for all safety assessments are provided in the SoA.

### **8.2.1. Physical Examinations**

- A complete physical examination will include, at a minimum, assessments of the Skin, Cardiovascular, Respiratory, Gastrointestinal and Neurological systems. Height and weight will also be measured and recorded.
- A brief physical examination will include, at a minimum, assessments of the skin, lungs, cardiovascular system, and abdomen (liver and spleen).
- Investigators should pay special attention to clinical signs related to previous serious illnesses.

### **8.2.2. Vital Signs**

- Tympanic temperature, pulse rate, respiratory rate, and blood pressure will be assessed.
- Vital signs (to be taken before blood collection for laboratory tests) will include tympanic-measured temperature, systolic and diastolic blood pressure, pulse and respiratory rate.
- Blood pressure and pulse measurements will be assessed in a semi-supine position with a completely automated device. Manual techniques will be used only if an automated device is not available.
- Blood pressure and pulse measurements should be assessed after at least 10 minutes of rest for the participant in a quiet setting without distractions (e.g., television, cell phones) and for at least 10 minutes prior to and 5 minutes after each time point for ECG extractions.

- Vital signs when measured in triplicate in the SoA blood pressure measurements and pulse (3 consecutive readings will be recorded at intervals of at least 1 minute). The average of the 3 readings will be recorded on the CRF.

### **8.2.3. Holter Monitoring**

Approximately 24-hour screening Holter Monitoring will be collected in all participants of the study. The 24-hour Holter Monitoring will be performed to eliminate participants with non-clinically overt cardiac arrhythmias. If necessary, additional or extended monitoring (e.g., telemetry or Holter) may be performed at the Investigator or Sponsor's discretion to further characterize any emerging safety signals.

### **8.2.4. Electrocardiograms**

#### **8.2.4.1. 12-lead safety ECGs**

Safety ECGs will be printed and interpreted on-site by the Investigator to ensure participant safety. Safety ECGs may be printed from the Global Instrumentation Holter device (see below). Refer to Section 7 for QTc withdrawal criteria and additional QTc readings that may be necessary (equipment may be used to print out ECG's for scheduled or for AE's). (if have the capability to print out ECGs, may be done). Holter Monitor ECG are collected and held for analysis not in real time. Where there are scheduled ECGs, collection or an AE that requires ECG collection, if the Holter ECG instrumentation allows for a printout of an instantaneous ECG, the Holter equipment may be used to collect.

#### **8.2.4.2. Cardiodynamic assessment (ECGs extracted from Holter recordings)**

The frequency of ECG data in the SAD and MAD arises from emerging literature suggesting frequent QT evaluation early in development may mitigate the need for a formal TQT study [Darpö, 2014]. ECGs will be extracted as shown in the SOA from the SAD and the MAD component of the study, not including the extension cohort. Should clinical development of GSK3882347 continue, an exploratory objective of this study is to assess the exposure-response relationship between GSK3882347 and QTcF following single and repeat dose administration.

The 12-lead Holter/ECG equipment will be supplied and supported by ERT. All continuous ECG (Holter) data will be collected using a Global Instrumentation (Manlius, NY, USA) M12R ECG continuous 12-lead digital recorder. The continuous 12-lead digital ECG data will be stored onto SD memory cards. In case the cardiodynamic evaluation is undertaken, 12-lead ECGs will be extracted in replicates from the continuous ECG recording at pre-determined time points as defined in the SOA and will be read centrally by ERT.

The following principles will be followed in ERT's core laboratory:

- ECG analysts are blinded to the participant, visit and treatment allocation
- Baseline and on-treatment ECGs for a participant will be over-read on the same lead and will be analyzed by the same reader.

- The primary analysis lead is lead II. If lead II is not analyzable in any specific participants, then primary lead of analysis will be changed to another lead for the entire participant data set.

Additional details can be found in the SRM.

### **8.2.5. Clinical Safety Laboratory Assessments**

- Refer to [Appendix 2](#) for the list of clinical laboratory tests to be performed and to the SoA for the timing and frequency.
- The investigator must review the laboratory report, document this review, and record any clinically relevant changes occurring during the study in the AE section of the CRF. The laboratory reports must be filed with the source documents. Clinically significant abnormal laboratory findings are those which are not associated with the underlying disease, unless judged by the investigator to be more severe than expected for the participant's condition.
- All laboratory tests with values considered clinically significantly abnormal during participation in the study or within 14 days after the last dose of study intervention should be repeated until the values return to normal or baseline or are no longer considered significantly abnormal by the investigator or medical monitor.
- If such values do not return to normal/baseline within a period of time judged reasonable by the investigator, the etiology should be identified and the sponsor notified.
- All protocol-required laboratory assessments, as defined in [Appendix 2](#), must be conducted in accordance with the laboratory manual and the SoA.

## **8.3. Adverse Events and Serious Adverse Events**

The definitions of an AE or SAE can be found in [Appendix 3](#).

The investigator and any qualified designees are responsible for detecting, documenting, and reporting events that meet the definition of an AE or SAE and remain responsible for following up AEs that are serious, considered related to the study intervention or the study, or that caused the participant to discontinue the study intervention (see Section 7).

### **8.3.1. Time Period and Frequency for Collecting AE and SAE Information**

- All SAEs will be collected from the signing of the informed consent form until the follow-up visit at the time points specified in the SoA (Section 1.3). However, any SAEs assessed as related to study participation (e.g., study intervention, protocol-mandated procedures, invasive tests, or change in existing therapy) or related to a GSK product will be recorded from the time a subject consents to participate in the study.
- All AEs will be collected from the start of intervention until [the follow-up visit] at the time points specified in the SoA (Section 1.3).

- Medical occurrences that begin before the start of study intervention but after obtaining informed consent will be recorded on the Medical History/Current Medical Conditions section of the case report form (CRF) not the AE section.
- All SAEs will be recorded and reported to the sponsor or designee immediately and under no circumstance should this exceed 24 hours, as indicated in [Appendix 3](#). The investigator will submit any updated SAE data to the sponsor within 24 hours of it being available.
- Investigators are not obligated to actively seek AEs or SAEs after the conclusion of the study participation. However, if the investigator learns of any SAE, including a death, at any time after a participant has been discharged from the study, and he/she considers the event to be reasonably related to the study intervention or study participation, the investigator must promptly notify the sponsor.

### **8.3.2. Method of Detecting AEs and SAEs**

- The method of recording, evaluating, and assessing causality of AEs and SAEs and the procedures for completing and transmitting SAE reports are provided in [Appendix 3](#).
- Care will be taken not to introduce bias when detecting AE and/or SAE. Open-ended and non-leading verbal questioning of the participant is the preferred method to inquire about AE occurrence.

### **8.3.3. Follow-up of AEs and SAEs**

After the initial AE/SAE report, the investigator is required to proactively follow each participant at subsequent visits/contacts. All SAEs, will be followed until the event is resolved, stabilized, otherwise explained, or the participant is lost to follow-up (as defined in Section [7.4](#)). Further information on follow-up procedures is given in [Appendix 3](#).

### **8.3.4. Regulatory Reporting Requirements for SAEs**

- Prompt notification by the investigator to the sponsor of a SAE is essential so that legal obligations and ethical responsibilities towards the safety of participants and the safety of a study intervention under clinical investigation are met.
- The sponsor has a legal responsibility to notify both the local regulatory authority and other regulatory agencies about the safety of a study intervention under clinical investigation. The sponsor will comply with country-specific regulatory requirements relating to safety reporting to the regulatory authority, Independent Ethics Committees (IEC), and investigators.
- Investigator safety reports must be prepared for suspected unexpected serious adverse reactions (SUSAR) according to local regulatory requirements and sponsor policy and forwarded to investigators as necessary.

- An investigator who receives an investigator safety report describing a SAE or other specific safety information e.g., summary or listing of SAE) from the sponsor will review and then file it along with the Investigator's Brochure and will notify the IEC, if appropriate according to local requirements.

### **8.3.5. Pregnancy**

- Details of all pregnancies in female partners of male participants will be collected where conception may have occurred during or up to 5 days after dosing.
- If a pregnancy is reported, the investigator should inform GSK within 24 hours of learning of the pregnancy and should follow the procedures outlined in [Appendix 4](#).
- Abnormal pregnancy outcomes (e.g., spontaneous abortion, fetal death, stillbirth, congenital anomalies, ectopic pregnancy) are considered SAEs.

### **8.4. Treatment of Overdose**

For this study, any dose of GSK3882347 greater than 900 mg within a 24-hour time period ( $\pm 1$  hour) will be considered an overdose.

Sponsor does not recommend specific treatment for an overdose.

In the event of an overdose, the investigator should:

- Contact the Medical Monitor immediately.
- Closely monitor the participant for AE/SAE and laboratory abnormalities until GSK3882347 can no longer be detected systemically (at least 5 days).
- Obtain a plasma sample for PK analysis if requested by the Medical Monitor (determined on a case-by-case basis).
- Document the quantity of the excess dose as well as the duration of the overdosing in the CRF.

Decisions regarding dose interruptions or modifications will be made by the investigator in consultation with the Medical Monitor based on the clinical evaluation of the participant.

### **8.5. Pharmacokinetics**

#### **8.5.1. Blood Sample Collection**

- Whole blood samples of approximately 1 mL will be collected for measurement of plasma concentrations of GSK3882347 as specified in the SoA. The timing of PK samples may be altered and/or PK samples may be obtained at additional time points to ensure thorough PK monitoring. A maximum of 10 samples may be collected at additional time points during the study if warranted and agreed upon between the investigator and the sponsor. Instructions for the collection and handling of biological samples will be provided by the sponsor. The actual date and time (24-hour clock time) of each sample will be recorded.

- A 1 mL of whole blood sample will be collected for metabolite profiling on Day 1 in Part 1 (excluding food effect groups); and 4 mL in Part 2 as specified in the SoA.
- The metabolite profiling of the plasma samples will be conducted under separate protocols and results are reported separately according to the IV/IVT DMPK, GSK protocols.
- Samples will be used to evaluate the PK of GSK3882347. Samples collected for analyses of study intervention plasma concentration may also be used to evaluate safety or efficacy aspects related to concerns arising during or after the study. Residual PK Plasma samples may be analyzed for other compound-related metabolites and the results reported under a separate IV/IVT, GSK protocols.
- Genetic analyses will not be performed on these whole blood samples unless consent for this was included in the informed consent. Participant confidentiality will be maintained. Participant confidentiality will be maintained. At visits during which whole blood samples for the determination of GSK3882347 will be taken, one sample of sufficient volume can be used.

Drug concentration information that would unblind the study will not be reported to investigative sites or blinded personnel until the study has been unblinded.

Details of blood sample processing, storage and shipping procedures are provided in the SRM or equivalent.

#### **8.5.2. Urine Sample Collection**

- Urine samples will be collected up to 96 hours from dosing in Part 1 and up to 24 hours from dosing on Days 1 and 7 in Part 2 MAD (exact times are specified in the SoA). The time will be recorded for each urine sample collected, and the total urine volume for each subject will be recorded over the collection time period.
- From each urine PK interval, a 1 mL aliquot of urine will be collected for PK analysis and stored at approximately 70°C or colder. **Note: it is highly important that the urine sample is thoroughly mixed using several repeat inversions of the sample prior to removal of the 1 mL aliquot for PK analysis.**
- The metabolite profiling of the urine samples will be conducted under separate protocols and results are reported separately according to the IV/IVT DMPK, GSK protocols.
- The timing of urine samples may be altered and/or samples may be obtained at additional time points to ensure thorough PK monitoring.

Details of urine sample processing, storage and shipping procedures are provided in the SRM.

## **8.6. Plasma Sample for CYP3A4 Enzyme Activity**

Plasma derived from 3 mL blood samples in Part 2 (as in the SoA Table, see Section 1.3) will be analyzed for 4 $\beta$ -hydroxycholesterol and cholesterol as a potential *in vivo* marker of CYP3A4 enzyme activity.

Details on CYP3A4 enzyme activity marker plasma sample collection, processing, storage and shipping procedures are provided in the SRM.

Plasma samples collected in the fasted state at Baseline and on Day 8 (i.e. collected 24 hours post dosing on Day 7) will be analyzed using a validated, specific, and sensitive liquid chromatography–mass spectrometry (LC-MS/MS) method to determine concentrations of 4 $\beta$ -hydroxycholesterol and total cholesterol. A comparison will be made between the ratio of 4 $\beta$ -hydroxycholesterol: cholesterol at baseline and on Day 8 to assess potential changes in CYP3A4 enzyme activity following GSK3882347 treatment.

Analysis will be performed at a bioanalytical site (to be detailed in the SRM) under the control of PTS-IVIVT and Third Party Resource, GlaxoSmithKline.

## **8.7. Pharmacodynamics**

### **8.7.1. Microbiome Assessments**

Stool specimens for potential microbiome assessment will be obtained at the time points as specified in the SoA. The actual date and time of each sample collection will be recorded.

Collection, processing, storage, and shipping procedures for microbiome specimens are provided in the Central Laboratory Manual.

## **8.8. Genetics**

A 6 mL blood sample for DNA isolation will be collected from participants who have consented to participate in the genetics analysis component of the study. Participation is optional. Participants who do not wish to participate in the genetic research may still participate in the study.

In the event of DNA extraction failure, a replacement genetic blood sample may be requested from the participant. Signed informed consent will be required to obtain a replacement sample unless it was included in the original consent.

See [Appendix 5](#) for Information regarding genetic research. Details on processes for collection and shipment can be found in the Central Laboratory Manual and destruction of these samples can be found in SRM.

## **8.9. Biomarkers**

Biomarkers are not evaluated in this study.

## **8.10. Health Economics/Medical Resource Utilization and Health Economics**

Health Economics/Medical Resource Utilization and Health Economics parameters are not evaluated in this study.

## **9. STATISTICAL CONSIDERATIONS**

Statistical analyses will be performed by, or under the direct auspices of, Biostatistics, GlaxoSmithKline.

Reporting of study data will be performed in accordance with applicable GSK and/or contract research organization (CRO) standards.

Complete details of the planned statistical analyses will be provided in the Reporting and Analysis Plan (RAP).

Any deviations from the planned analyses will be described in a RAP addendum and justified in the final integrated clinical study report.

### **9.1. Statistical Hypotheses**

No formal statistical hypotheses will be tested.

### **9.2. Sample Size Determination**

Approximately 56 randomized participants will be recruited for the entire study, including 16 evaluable participants in the SAD part (Part 1) with 6 active and 2 placebo per cohort, and 40 evaluable participants in the MAD part (Part 2) with 8 active and 2 placebo per cohort. Additional participants may be recruited as replacement for withdrawn participants including those for COVID-19.

A preliminary PK/PD target was determined as a trough GSK3882347 urine concentrations in the range of 5 to 30  $\mu$ M, where 5  $\mu$ M represent the minimum trough concentration potentially associated with efficacy in the clinic.

Since this is a first in human study, sample size justification is based on data predicted from animal studies. [Table 9](#) and [Table 10](#) contain the predicted human urine trough concentration based on dog and rat PK data under 4 dose levels and 3 urine volumes. The assumption is the urine trough concentration follows log-normal distribution with mean value listed in [Table 9](#) and [Table 10](#). The probabilities of successfully achieving  $\geq 5$   $\mu$ M in urine under each setting are presented in [Table 11](#) and [Table 12](#).

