**Table 4 Part 2 – 7-Day Repeat Dose Escalation (Days 2 through 6 and Day 8 to 12)**

Procedure	Study Days								Notes
	2 (24hrs post-Day 1 dose)	3	4	5	6	8 (24 hrs post-Day 7 dose)	9-12		
Brief physical examination	X	X	X	X	X		X	X*	*Upon discharge
Administration of study intervention	X	X	X	X	X				No minimum time interval is required between the sentinels at each dose level. Approximately 15 minutes will be observed between the dosing of the remaining participants
AE Review	Continuous review								
SAE Review	Continuous review								
Ad hoc COVID-19 testing based on clinical presentation and site procedures	Continuous review							X*	*Sample collected just prior to discharge for COVID-19 testing
Concomitant medication review	Continuous review								

Procedure	Study Days								Notes
	2 (24hrs post-Day 1 dose)	3	4	5	6	8 (24 hrs post-Day 7 dose)	9-12		
Vital signs (BP, HR, tympanic temperature, respiration rate)	X		X	X	X	X		X	Single measurements will be obtained within 1-hour pre-dose and daily in the morning on days 9-12 until discharge.  Timings will be reviewed as cohorts progress and may be adjusted to ensure appropriate measurements relative to peak concentrations for subsequent cohorts.
12-lead safety electrocardiogram	X		X	X	X	X		X	Single 12-lead safety ECGs will be obtained within 1 hour before pre-dose and daily in the morning on days 9-12 until discharge.

Procedure	Study Days								Notes
	2 (24hrs post-Day 1 dose)	3	4	5	6	8 (24 hrs post-Day 7 dose)	9-12		
Continuous cardiac monitoring**	X					X			**Participants will be semi-supine resting for at least 10 minutes prior to and 5 minutes after each time point for ECG extractions.  When ECG extractions coincide with safety ECGs, vital signs assessment and blood draws, procedures should occur in that order.
Clinical chemistry (including liver and kidney chemistries), hematology, and urine tests (including urine creatinine)		X	X	X	X		X	X*	*Just prior to discharge.
PK Blood Sample	X		X*	X*	X*	X*	X		*Trough PK samples
4β-hydroxycholesterol sampling						X			Sample to be taken at 24hr post AM dose on Day 7. Sample should be in a fasted state.
PK Metabolite Sample	X						X		
PK Urine Sample	X		X*	X*	X*	X*	X		*Trough PK samples

Procedure	Study Days								Notes
	2 (24hrs post-Day 1 dose)	3	4	5	6	8 (24 hrs post-Day 7 dose)	9-12		

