### 2.1. Study Rationale

The goal of this study is to evaluate the safety, tolerability and pharmacokinetic properties (including food effect) of GSK3882347 to enable clinical development of the molecule as an antibiotic-sparing treatment for uncomplicated urinary tract infections.

Bacteria possess adhesins, which are cell-surface components or appendages that facilitate adhesion or adherence to other cells or to surfaces. GSK3882347 is a potent and specific competitive antagonist of the *Escherichia coli* type 1 pilus adhesin molecule FimH, designed to disrupt the interaction between FimH and mammalian mannose-rich glycoproteins, such as uroplakin Ia and integrins in the bladder epithelium and other epithelia.

GSK3882347 is being developed as an antibiotic-sparing medicine to treat or prevent infection of the bladder mucosa, via inhibition of FimH protein function on UPEC, which cause approximately 85% of all urinary tract infections. It is anticipated that the use of GSK3882347 will help combat the increasing antimicrobial resistance (AMR) to traditional antibiotics that threatens to increase greatly the economic burden, morbidity and mortality associated with bacterial infections [O'Neill, 2016].

Preclinical data in a murine urinary tract infection (UTI) model supports the use of a FimH antagonist in both the treatment and prevention of uncomplicated UTI (uUTI) in both infection naïve mice and previously infected mice (a recurrent UTI (rUTI) model). *In vitro* data indicate that GSK3882347 is an effective antagonist of FimH in a broad range of clinical UPEC strains. Further, GSK3882347 was effective against a subset of these strains representing all the major UPEC FimH alleles in both the murine UTI treatment model and in an *in situ* human bladder tissue binding assay. GSK3882347 inhibited binding in a concentration-dependent manner by >95% at 30  $\mu$ M (or less). *In vivo* efficacy studies were also completed using the acute therapeutic model in mice with UPEC strain UTI89 to correlate microbiological efficacy and urinary exposure. A preliminary PK/PD target for GSK3882347 was determined as the maintenance of a trough concentration of  $\geq$ 5  $\mu$ M in urine for the duration of the dosing period. Based on the studies described above, a target Cmin concentration range of 5-30  $\mu$ M was defined to support dose selection in this study.

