#### 4.3.2. Predicted Efficacious Dose

An *in-situ* binding assay was used to characterize GSK3882347 mediated inhibition of UPEC binding to healthy or inflamed human bladder epithelium. Although there was much variation in the level of binding by the strains to human bladder tissue- either healthy or inflamed, all strains tested could be inhibited by GSK3882347 and in the clear majority of cases tissue binding was inhibited by >95% at 30 µM (or less), relative to vehicle controls. *In vivo* efficacy studies were also completed using the acute therapeutic model in mice with UPEC strain UTI89 to correlate microbiological efficacy and urinary exposure. A preliminary PK/PD target for GSK3882347 was determined as the maintenance of a trough concentration of ≥5 µM in urine for the duration of the dosing period. Importantly, achieving this target provided maximal efficacy regardless of dosing

regimen (regimens evaluated: QD, BID, and TID). Based on the studies described above, a target Cmin concentration range of 5-30  $\mu$ M was defined to support dose selection in this study.

The predicted efficacious doses for humans were calculated using the PBPK model based on the target urine Cmin range of 5-30  $\mu$ M at day 1 and considering the difference in the rat and dog pharmacokinetics (see [Table 7](#)).

**Table 7 Anticipated Therapeutic Dose Range Considering Different Target Urine Cmin and Human Predicted Pharmacokinetics Based on Rat and Dog Pre-clinical Data**

Predicted Human Therapeutic Dose		
Urine target C min ( $\mu$ M)	Based on Dog PK	Based on Rat PK
5	50 mg	300 mg
30	300 mg	650 mg

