**Table 11 Probability (%) of All 8 Participants (90%) Achieving Urine Trough  $\geq 5\mu\text{M}$  PK Based on Dog Data**

Dose (mg)	Avg urine vol	Low urine vol	High urine vol
900 QD	98.16	99.59	93.77
500 QD	95.24	98.59	85.14
150 QD	49.86	76.36	22.78
50 QD	2.22	14.44	0.25

\*SD of 1.04 from study 206899 is used as the SD of log transformed data.

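### Do the loose labels on the urine-trough probabilities in Section 9.2 (Tables 11 and 12) call for a change to the sample-size plan?

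*Protocol*

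**What the plan says.** Section 9.2 plans eight active and two placebo participants per Part 2 cohort. Its model for the urine trough is: "The assumption is the urine trough concentration follows log-normal distribution with mean value listed in" Tables 9 and 10, which give predictions from dog and rat data at four doses and three urine volumes. Tables 11 and 12 share a title that begins "Probability (%) of All 8 Participants (90%) Achieving Urine Trough", with a threshold of 5 µM. A footnote to each gives 1.04 as the SD of the log-transformed data.

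Sections 2.1 and 4.3.2 set a preliminary target that "was determined as the maintenance of a trough concentration of" at least 5 µM "in urine for the duration of the dosing period". Both sections then give a Cmin range of 5 to 30 µM for dose selection, with no duration attached. Section 4.3.2 computes its predicted doses "at day 1 and considering the difference in the rat and dog pharmacokinetics".

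On sampling, Section 8.5.2 describes Part 2 urine collection "up to 24 hours from dosing on Days 1 and 7 in Part 2 MAD (exact times are specified in the SoA"). The urine row of Table 4 in the Schedule of Activities (SoA) also carries starred entries, noted as "Trough PK samples", between the Day 2 and Day 8 samples. Section 3 makes the 22–24 h urine concentration a primary endpoint. The primary row in Section 9.4.2 names the amount excreted, the fraction excreted and renal clearance.

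**The concern.** A reader could stumble over Section 9.2 in four places.

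- The mean of a log-normal variable usually denotes the arithmetic mean, and that reading does not give the printed probabilities.
- The 90% sits beside a statement about all eight participants. Eight of eight is 100% and seven of eight is 87.5%, so it describes neither.
- The day of the predicted trough is not named.
- The tables count one trough per participant, while the target in Sections 2.1 and 4.3.2 is a trough held throughout dosing. Someone could take the tables as the chance of meeting that target, which is lower unless troughs within a participant are perfectly correlated or rise well clear of 5 µM.

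If Section 8.5.2 were followed in place of the SoA, the intermediate trough samples, which would show whether the concentration is maintained, might be missed. An analyst working only from Section 9.4.2 might also leave out a primary urine endpoint.

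**Working it through.** **Inputs.** Predicted trough c from Tables 9 and 10; log-scale SD 1.04 from the footnotes to Tables 11 and 12; threshold 5 µM and n = 8 from Section 9.2.

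**Reproducing the printed tables.** With c as the geometric mean (median), one participant succeeds with probability p = Φ(ln(c/5)/1.04), and all eight succeed with probability p^8. At the average urine volume:

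| Case | c (µM) | p | p^8 | Printed |
|---|---|---|---|---|
| Dog 900 mg | 93.6 | 0.9976 | 98.08% | 98.16% |
| Dog 500 mg | 65.6 | 0.9933 | 94.80% | 95.24% |
| Dog 150 mg | 20.9 | 0.9155 | 49.34% | 49.86% |
| Dog 50 mg | 6.94 | 0.6237 | 2.29% | 2.22% |
| Rat 900 mg | 30.6 | 0.9592 | 71.68% | 71.8% |
| Rat 500 mg | 10.7 | 0.7678 | 12.07% | 11.8% |

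For dog 150 mg: ln(20.9/5) = 1.4303; 1.4303/1.04 = 1.3753; Φ = 0.9155; 0.9155^8 = 49.3%. Over all 24 cells the largest gap is 0.60 points (dog 50 mg, low volume: 13.84% against 14.44%).

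**Alternative readings.**

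- Arithmetic mean: p = Φ((ln(c/5) − 1.04²/2)/1.04). Dog 150 mg gives p = 0.8038 and p^8 = 17.4%; rat 900 mg gives 39.1%. The miss reaches about 33 points (71.8 − 39.1).
- At least seven of eight: p^8 + 8p^7(1 − p). Dog 150 mg gives 85.8%. The miss reaches about 39 points (rat 500 mg, low volume: 76.3% against 37.1%).

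Of the readings tried, only the geometric mean with eight of eight fits, so the tables settle their own ambiguity.

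**Maintained trough.** The protocol gives no within-participant correlation r, so r = 0.9, 0.5 and 0 is an assumed range. For k equally correlated troughs at a constant c, the probability that one participant stays at or above 5 µM is q = ∫φ(z)·Φ((ln(c/5)/1.04 + √r·z)/√(1 − r))^k dz, and the cohort probability is q^8.

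| Case | Printed | r = 0.9 | r = 0.5 | r = 0 |
|---|---|---|---|---|
| Rat 900 mg, 6 troughs | 71.8% | 49.8% | 25.5% | 13.6% |
| Rat 900 mg, 7 troughs | 71.8% | 48.0% | 22.0% | 9.7% |
| Dog 900 mg, 6 troughs | 98.16% | 95.0% | 90.5% | 89.0% |

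Suppose instead that Table 9 holds Day 1 values and that troughs build up by the AUC ratio in Table 5 (107/40.5 = 2.64). Dog 900 mg over six troughs then gives 98.0%, 97.3% and 97.2%, close to the printed 98.16%. The answer depends on inputs the protocol does not supply: r, the day, whether the AUC ratio carries over to urine, and six sampled troughs or seven doses.

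**Sampling and endpoint passages.** Section 8.5.2 does not confine collection to Days 1 and 7. It describes the 24-hour collections with volume recorded, points to the SoA for exact times, and allows additional time points. Section 8 states: "Adherence to the study design requirements, including those specified in the SoA, is essential and required for study conduct". The trough samples in Table 4 therefore stand. Section 9.4.2 lists derived parameters, whereas the 22–24 h value is a measured concentration that is already primary in the Synopsis and in Section 3.

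**The case for a change.** The best argument for a change is that Section 9.2 offers these tables as its sample-size justification. A justification should state its inputs, event and day, so that it can be reproduced and is not taken for something else. The edits would be cheap: write geometric mean, name the day, define or remove the 90%, and note that the tables concern a single trough. The 90% in particular has no explanation anywhere in the protocol.

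That much stands as a comment on drafting. The stronger claim, that the tables overstate the chance of meeting the protocol's own target, does not. Section 9.2 claims only the probability of reaching 5 µM in each setting. The 5 to 30 µM range it uses also appears in Sections 2.1 and 4.3.2 without a duration. A probability for all troughs together would be an added analysis resting on an undocumented correlation. It would not correct a printed figure. It is also an overstatement that Section 9.2 cannot be reproduced: every number needed is printed there, and pairing a log-scale SD with a log-scale centre is the natural first attempt.

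**Conclusion.** No change follows. The tables are correctly computed as single-trough, eight-of-eight probabilities, within 0.60 points in every cell. What remains is clerical: a missing qualifier on the mean, a stray 90% and an unnamed day. Section 9.1 tests no hypothesis, and eight per cohort is not solved from these probabilities, so the sample size would be the same under any labelling.

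The maintained-trough figures (for rat 900 mg over six troughs, 49.8% down to 13.6%) show how one could misread the tables, but they rest on assumed correlations and leave the plan's own statement intact. The samples that would show maintenance are already in Table 4, and Section 8 makes the SoA binding. The 22–24 h urine concentration is primary in Section 3; its summary is the kind of detail Sections 9 and 9.4.3 leave to the Reporting and Analysis Plan, which was not available here.

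This conclusion assumes that the site works from the SoA and that the analysis plan takes its endpoints from Section 3. Table 4 is hard to read column by column in the available text, but the starred trough entries and their note are clear.
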